8.7.1.2.5 Primary and Secondary Endpoints

Analysis of primary efficacy endpoint

The primary endpoint of this trial is a composite of all cause-death or any use of invasive mechanical ventilation up to 28 days or hospital discharge.

Invasive mechanical ventilation is defined as patients who are intubated or have a tracheostomy tube and are receiving positive pressure ventilation. Patients who will be discharged from hospital before day 28 will be considered as non-event after confirmation by telephone interview that they are alive at day 28. Patients who will be discharged from hospital or early terminated before Day 28 will be considered having an event on the day of discharge or early termination, if a telephone interview was not possible and/or no information about alive/death status is known.

Hypothesis to be tested:

H0: $p_{APN01} = p_{Placebo}$

H1: $p_{APN01} \neq p_{Placebo}$

H0 will be tested using a Chi-squared test. The level of significance is 5% (two-sided). In addition, logistic regression analyses will be conducted considering additional co-factors (will be detailed in the statistical analysis plan).

Analysis of secondary efficacy endpoints

Secondary efficacy variables will be tested descriptively and in an exploratory manner.

1. Log transformed levels of Lactate dehydrogenase (LDH) at day 5 as a surrogate marker for organ damage

Log transformed levels of LDH will be analyzed using linear regression adjusted for baseline log levels of LDH, center and minimization factors.

95% confidence intervals will be additionally calculated.

Statistical procedures to check on a normal distributed of data, to be applied in case of non-normally distributed data, and to verify and handle minimization factors will be described in the statistical analysis plan, which will be finalized prior to unblinding.

2. 28-day mortality (all cause death)

The percentage of patients who have died at Day 28 will be presented by treatment group. Patients who will be discharged from hospital or early terminated before Day 28 will be considered having an event on the day of discharge or early termination, if a telephone interview was not possible and/or no information about alive/death status is known. The Chi-squared or Fisher's exact test will be used to compare proportions. 95% CIs will be additionally calculated. Logistic regression analyses will be conducted considering additional co-factors (will be detailed in the statistical analysis plan).

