2.2 Secondary Efficacy Endpoints

The following secondary efficacy parameters will be analyzed:

- Log transformed levels of lactate dehydrogenase (LDH) at Day 5 as a surrogate marker for organ damage (powered secondary endpoint)
- 28-day mortality (all cause death)
- Ventilator-free days (VFD) (up to 28 days or hospital discharge)
- Proportion of responders, defined as ≥ 2 improvement in WHO's 11-Point Score system at Day 7, 10, 14 and 28
- Time to death (all cause)
- Proportion of patients with any use of invasive mechanical ventilation (up to 28 days or hospital discharge)
- Time to first use of invasive mechanical ventilation (up to 28 days or hospital discharge)
- Absolute values and absolute change in PaO₂/FiO₂ ratio over time
- Absolute values and absolute change in modified Sequential organ failure assessment score (mSOFA score) over time
- Time to a 2-point decrease in WHO's 11-Point Score system
- Absolute values and absolute change in lymphocyte counts over time
- Absolute values and absolute change in C-reactive protein levels over time
- Absolute values and absolute change in D-dimer over time
- Absolute values and absolute change in log transformed levels of LDH over time
- Time to hospital discharge
- Change in viral RNA over time

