4.4.2 Analysis of Secondary Efficacy Endpoints

Log transformed levels of lactate dehydrogenase (LDH) at Day 5 as a surrogate marker for organ damage (powered secondary endpoint)

Results of LDH will be converted to standard unit before any calculation if needed. Conversion of all lab values will be described in a separate document 'Conversion_3570_VX-X_2020-MM-DD'. Standardized results will be log transformed for this endpoint.

Log transformed levels of LDH will be analyzed using linear regression adjusted for baseline log levels of LDH, center and age. 95% confidence intervals will be additionally calculated.

In protocol the wording of "minimization factors" is used: Stratification factors from the randomization are used in models as covariates.

Before application of the linear regression, it will be checked if the residuals are approximately normally distributed (QQ-Plot, Shapiro Wilk test). If there are no major violations of the normal distribution the model can be applied. If there are major violations available only descriptive analyses will be displayed.

Point estimate together with standard error and two-sided 95% confidence interval as well as p-value (two-sided) will be reported.

28-day mortality (all cause death)

The percentage of patients who have died at Day 28 will be presented by treatment group.

The following cases may occur:

- Patient discharged from hospital **and** discontinued before Day 28, will be followed up by telephone interview to check whether they are alive or dead, if unclear as no telephone interview available, death is assumed (worst case) at last available date of early termination, hospitalization or hospital discharge
- No discharge from hospital, **but** early discontinuation before Day 28 will be followed up by telephone interview to check whether they are alive or dead, if unclear as no telephone interview available, death is assumed (worst case) at date of early termination
- Discharged from hospital, **but** no discontinuation before Day 28: No telephone interview, but regular entry at Day 28 about alive/death status

Chi-squared test or Fisher's exact test

Proportion of responder, i.e. those patients that died, as well as the p-value (two-sided) will be reported.

Logistic regression

The following co-factors will be included in the logistic regression:

- ❑ Arterial hypertension
- ❑ Diabetes

- ❑ Coronary artery disease
- ❑ Age (<65 years vs. >=65 years)
- ❑ Center

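### An undefined normality rule can remove the adjusted Day 5 LDH comparison, although non-normal residuals do not invalidate that comparison at the planned size

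*SAP*

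**What the plan says.** SAP 2.2 lists sixteen secondary efficacy endpoints. Log LDH at Day 5 comes first and is the only one called a "powered secondary endpoint".

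SAP 4.4.2 sets out its analysis in four steps:

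- Model: "Log transformed levels of LDH will be analyzed using linear regression adjusted for baseline log levels of LDH, center and age".
- Check: "it will be checked if the residuals are approximately normally distributed (QQ-Plot, Shapiro Wilk test").
- If the check shows no major violation, the model is applied: "Point estimate together with standard error and two-sided 95% confidence interval as well as p-value (two-sided) will be reported".
- Otherwise: "If there are major violations available only descriptive analyses will be displayed".

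The SAP does not say what makes a violation major, how the plot and the test are to be combined, or who decides.

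Protocol 8.7.1.2.5 had left this to the SAP. It says that statistical procedures "to be applied in case of non-normally distributed data, and to verify and handle minimization factors will be described in the statistical analysis plan". SAP section 5 lists two changes from the protocol, and neither concerns this rule. For ventilator-free days, the same SAP section plans a Wilcoxon test and bootstrap intervals.

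**The concern.** The rule makes the reporting of a treatment comparison depend on a property that the comparison hardly needs. With about 90 patients per arm, the estimated treatment coefficient is close to normally distributed even when individual residuals are not. Shapiro-Wilk answers a different question, and at this size it picks up departures that do no harm to the contrast.

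At stake are the adjusted difference in log LDH, its standard error, its 95% interval and its p-value. LDH is the only efficacy measure named in the secondary objectives. Because the word major has no definition, reporting or withholding this result is a matter of judgement. If the model is fitted as specified, with treatment in it, the residuals exist only after unblinding, so that judgement would be made with the treatment codes known.

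**Working it through.** **1. The plan's own figure.** The only power calculation is for the primary composite (Protocol 8.7.2): 50% versus 30%, two-sided 0.05, 80% power. With a pooled rate of 0.40:

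n per group = [1.960 × √(2 × 0.40 × 0.60) + 0.842 × √(0.50 × 0.50 + 0.30 × 0.70)]² / 0.20² = (1.358 + 0.571)² / 0.04 ≈ 93.

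This matches the plan. No SD, target difference or power is given for LDH. By normal approximation, the difference detectable with 80% power is (1.960 + 0.842) × √(2/n) SDs. That is 0.40 SD at 100 per group and 0.51 SD at 60 per group.

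**2. The simulated model.** Log LDH was regressed on treatment, baseline, dichotomous age and center as fixed effects, with 1:1 allocation and no treatment effect. About 40 centers comes from SAP section 1. A total of 180 assumes that 90% of the 200 enrolled have a Day 5 value; SAP 4.7 imputes nothing. The model has 4 + 39 = 43 coefficients, which leaves 137 residual degrees of freedom at n = 180 and 157 at n = 200. The error shapes and the 5% Shapiro-Wilk cut-off are assumptions.

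**3. n = 180, 40 centers.** The size of the ordinary regression test was about 4.5 to 5.7% for every shape, including among the trials that Shapiro-Wilk would discard. Shapiro-Wilk rejected in about 70% (t(5)), 66% (gamma, shape 8), 74% (5% contamination) and 100% (exponential). Other runs of the same design, with equal or uneven center sizes, gave 61 to 72%, 58 to 71% and 67 to 73% for the first three.

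The center term matters. Without it the rates rise to about 76–77%, 91–92% and 77–78%, because residuals from a model with many fitted terms look more normal than the errors behind them. The center-adjusted rates are the relevant ones.

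**4. Other sizes, 3,000 null trials per cell.**

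| Errors | n=200, 40 centers: size / coverage / S-W rejects | n=120, 30 centers: size / coverage / S-W rejects |
|---|---|---|
| normal | 5.1% / 94.9% / 5.1% | 5.2% / 94.8% / 4.5% |
| t(5) | 4.8% / 95.2% / 63.0% | 4.5% / 95.5% / 42.3% |
| t(3) | 5.6% / 94.4% / 93.6% | 4.9% / 95.1% / 77.1% |
| gamma(4) | 5.0% / 95.0% / 90.3% | 5.4% / 94.6% / 61.7% |
| exponential | 5.3% / 94.7% / 100% | 5.1% / 94.9% / 97.8% |
| lognormal | 4.1% / 95.9% / 100% | 4.6% / 95.4% / 99.9% |
| 10% shifted by 3 SD | 4.5% / 95.5% / 84.6% | 4.6% / 95.4% / 53.4% |

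The Monte Carlo standard error at 5% is √(0.05 × 0.95 / 3000) = 0.4 percentage points. Only the lognormal cell at n = 200 lies more than two standard errors from 5%, and it errs on the conservative side. Power at n = 200 for an assumed 0.45 SD difference was 81% (normal), 84% (t(3)) and 80% (exponential).

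**5. How much depends on the missing threshold.** At n = 180 with 40 centers, a cut-off of p < 0.001 was reached in 29 to 49% of the mildly non-normal trials. A cut-off of W < 0.95 was reached in 12–16% (t(5)), 1–4% (gamma(8)) and 20–27% (contamination). The SAP specifies none of these cut-offs.

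**6. HC3 as a remedy.** HC3 divides by one minus the leverage, and a center with one analysed patient gives leverage 1. With 180 patients spread evenly at random over 40 centers, the expected number of such centers is 180 × (39/40)^179 ≈ 1.9. At least one occurred in 88–89% of runs with equal expected center sizes, and in over 99% with uneven sizes.

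**The case against.** The strongest reply is that the rule is milder than a significance test. It asks for approximate normality, uses a plot as well as a test, and drops the model only for major violations of an outcome that is already log-transformed. This stands. A reader might infer that the analysis would be lost in 66 to 100% of trials with non-normal errors. The documents set no 5% rule, so those rates are not probabilities that the rule trips. It does not rescue the rule, however: exponential errors are a gross violation on any reading, and the regression remains valid under them too.

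Second, the stakes are limited. Protocol 8.7.1.2.5 makes all secondary endpoints exploratory, and no alpha or hierarchy depends on LDH. The powered label has no calculation behind it. This also stands.

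Third, a reader might infer that all treatment information on LDH would disappear. It would not. SAP 4.4.2 separately tabulates log LDH and its change by visit, and section 4 tabulates the arms separately. A crude difference, and from the SDs an approximate interval, could be worked out.

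Fourth, the SAP does say what happens with non-normal data, and it was finalized before unblinding. It is therefore too strong to say that the protocol's promise was ignored. What is missing is an inferential procedure: the SAP's only answer is to make no comparison.

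**Conclusion.** The point holds as a moderate one that should be fixed. An undefined rule can withhold the adjusted difference, confidence interval and p-value for the one secondary endpoint labelled as powered, on a ground that does not invalidate them. Test size stays at about 4.5 to 5.7% with 180 patients and 40 centers, and at 4.1 to 5.6% across the tabulated settings at n = 200 and n = 120.

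This rests on the error shapes tried, on independent errors with equal variance, and on Day 5 LDH being available for at least about 120 patients. Heteroscedasticity, extreme outliers and very small numbers were not examined. How often the rule would trip cannot be stated from the documents. The primary analysis and its conclusion are not affected.

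**What to change.** In SAP 4.4.2, delete the sentence that falls back to descriptive analyses, together with the sentence that makes the model conditional on the check. State instead that:

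- the adjusted regression difference at Day 5 is always reported, back-transformed to a ratio of geometric means, with its 95% CI and p-value;
- the QQ-plot and Shapiro-Wilk test serve as diagnostics only;
- if they show marked departure, a rank-based ANCOVA or a bootstrap CI is added as sensitivity analysis, which also supplies the procedure that the protocol called for.

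Do not name HC3 standard errors as the remedy unless small centers are pooled first, because HC3 is undefined with single-patient centers. The cost is one SAP sentence and one extra model run, with no new data.

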4.4.1 Analysis of Primary Efficacy Endpoint

The primary endpoint is a composite endpoint of all cause-death or invasive mechanical ventilation (up to 28 days or hospital discharge).

The following null hypothesis will be tested:

- $H_0: p_{APN01} = p_{Placebo}$

versus the alternative

- $H_1: p_{APN01} \neq p_{Placebo}$

H_0 will be tested using a Chi-squared test. The level of significance is 5% (two-sided). In addition, logistic regression analyses will be conducted considering additional co-factors.

All cause-death

The percentage of patients who have died at Day 28 will be presented by treatment group.

Patients with death from any cause will be used for this endpoint as part of responder. Patients who are still alive at Day 28 will be considered as non-event.

The following cases may occur:

- Patient discharged from hospital **and** discontinued before Day 28, will be followed up by telephone interview to check whether they are alive or dead, if unclear as no telephone interview available, death is assumed (worst case) at last available date of early termination, hospitalization or hospital discharge
- No discharge from hospital, **but** early discontinuation before Day 28 will be followed up by telephone interview to check whether they are alive or dead, if unclear as no telephone interview available, death is assumed (worst case) at date of early termination
- Discharged from hospital, **but** no discontinuation before Day 28: No telephone interview, but regular entry at Day 28 about alive/death status

Invasive mechanical ventilation (up to 28 days or hospital discharge)

Invasive mechanical ventilation is defined as patients who are intubated or have a tracheostomy tube and are receiving positive pressure ventilation. Patients with at least one invasive mechanical ventilation (event with type of ventilation 'Mechanical ventilation') up to 28 days or hospital discharge will be used for this endpoint as part of responder.

Chi-squared test

Proportion of responder, i.e. those patients that died or having an invasive mechanical ventilation (up to 28 days or hospital discharge), as well as the p-value (two-sided) will be reported.

Logistic regression

A logistic regression with the responder (yes/no) as independent variable will be applied.

The following co-factors will be included in the logistic regression:

- Arterial hypertension

- ❑ Diabetes
- ❑ Coronary artery disease
- ❑ Age (<65 years vs. >=65 years)
- ❑ Center

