The odds ratio along with its associated 95% confidence intervals will be reported.

Ventilator-free days (VFD) (up to 28 days or hospital discharge)

VFD will be calculated as follows:

$VFD = \text{maximum}((\text{Duration in the study [days]} - \text{Duration of ventilation [days]}); 0)$

i.e. if the duration of ventilation is greater than the duration in the study, VFD is set to 0.

Duration in the study [days] = Date of study completion/ discontinuation - Date of randomization + 1.

Patients who died before or on Day 28 will be censored at the day before death (Date of death - 1).

Duration of ventilation [days] = Sum of days with all required ventilations.

If ventilation started before randomization, the duration will be counted from the date of randomization. If ventilation started and/or ended after study completion/ discontinuation, the duration will be counted until date of study completion/ discontinuation.

If ventilation is ongoing and/or no stop date is available, the duration will be calculated until date of study completion/ discontinuation or date of death respectively.

VFD will be analyzed for both all patients as well as for the subgroup of patients who were alive at Day 28 or hospital discharge/early termination. For the analysis of all patients separate analyses will be conducted for patients who died: a) VFD will be set to 0, b) the observed VFD until death will be considered.

Summary tables will be generated by treatment group.

VFD will be compared using Wilcoxon rank sum test at a significance level of 5% (two-sided) and p-value (two-sided) will be reported.

In addition, bootstrap methods will be applied to calculate 95% confidence intervals and two-sided p-values for the difference in means between treatment groups.

Proportion of responders, defined as >= 2 improvement in WHO's 11-Point Score system at Day 7, 10, 14 and 28

Patients who will be not assessed from any cause (e.g. discharge from hospital, early termination, death or in-home visit) will be considered as non-responder.

Chi-squared test or Fisher's exact test

Proportion of responder, i.e. those patients that have >= 2 improvement in WHO's 11-Point Score system, as well as the p-value (two-sided) will be reported for Day 7, 10, 14 and 28.

Logistic regression

The following co-factors will be included in the logistic regression:

- ❑ Arterial hypertension
- ❑ Diabetes
- ❑ Coronary artery disease

- Age (<65 years vs. ≥65 years)
- Center

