Proportion of patients with any use of invasive mechanical ventilation (up to 28 days or hospital discharge)

Requirement and type of ventilation will be presented using frequency tables.

Chi-squared test or Fisher’s exact test

Proportion of responder, i.e. those patients that having an invasive mechanical ventilation (up to 28 days or hospital discharge), as well as the p-value (two-sided) will be reported.

Logistic regression

The following co-factors will be included in the logistic regression:

- Arterial hypertension
- Diabetes
- Coronary artery disease
- Age (<65 years vs. >=65 years)
- Center

The odds ratio along with its associated 95% confidence intervals will be reported.

Time to first use of invasive mechanical ventilation (up to 28 days or hospital discharge)

Time to first use of invasive mechanical ventilation [days] = Start date of first ventilation - Date of randomization.

If ventilation started before randomization, the time to first use will be set to 0 (minimal possible duration).

Patients without documented invasive mechanical ventilation who completed the study or was early terminated or discharged from hospital before Day 28 will be censored at the date of study completion, discontinuation or discharge from hospital respectively.

Time to first use of invasive mechanical ventilation (up to 28 days or hospital discharge) will be analyzed using Kaplan-Meier estimates and plots, log-rank test, and Cox proportional hazards model (adjusted for center and age to derive hazard ratios and corresponding 95% confidence intervals).

Kaplan-Meier estimates and Log-rank test

Kaplan-Meier table (product-limit “survival” estimates with 95%-CI, Standard error, Number of patient with event, Number of patient at risk) for Time to first use of invasive mechanical ventilation [days], Kaplan-Meier Summaries of Event/Censoring (Number of patient with event, Number of patient censored, Total number of patients), Quartile Estimates (Median Time to Event, 1st Quartile, 3rd Quartile, 95%-CI) and Kaplan-Meier table (“survival” estimates with 95%-CI) for Timepoint (28 days). Time to first use of invasive mechanical ventilation [days] will be displayed by a Kaplan-Meier-curve. Treatments groups will be compared with Log-rank test.

Cox proportional hazards model

The hazards ratio along with its associated 95% confidence intervals as well as parameter estimate and p-value (two-sided) will be reported.

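### For deaths, the two terms of the ventilator-free-days formula stop on different dates, and the SAP does not say how days are counted or which ventilation types count

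*SAP*

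**What the plan says.** SAP 4.4.2 defines VFD as the larger of zero and study duration minus ventilation duration, and explains the floor: "i.e. if the duration of ventilation is greater than the duration in the study, VFD is set to 0".

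- **Study duration** is an inclusive count: "Duration in the study [days] = Date of study completion/ discontinuation - Date of randomization + 1".
- **Study duration for deaths** stops a day early: "Patients who died before or on Day 28 will be censored at the day before death (Date of death - 1").
- **Ventilation duration** has one line: "Duration of ventilation [days] = Sum of days with all required ventilations". No day convention, overlap rule or ventilation type is given.
- **Ongoing ventilation, or no stop date:** "the duration will be calculated until date of study completion/ discontinuation or date of death respectively".
- **Deaths** are handled in two ways: "a) VFD will be set to 0, b) the observed VFD until death will be considered". A further analysis is restricted to patients alive at Day 28, discharge or early termination.

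VFD is compared by a Wilcoxon rank sum test at two-sided 5%, with bootstrap confidence intervals and p-values for the difference in means. Protocol 8.7.1.2.5 gives no counting rule for VFD, and SAP section 5 lists no change to it.

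Ventilation type is available in the data. SAP 4.4.1 selects on it for the primary endpoint, using "Patients with at least one invasive mechanical ventilation (event with type of ventilation" equal to mechanical ventilation. For the proportion ventilated, SAP 4.4.2 adds: "Requirement and type of ventilation will be presented using frequency tables".

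**The concern.** A difference between two day counts is right only if both counts cover the same interval under the same convention. For deaths they do not: the ventilation term can include the day of death, which the study-duration term leaves out. A patient can therefore lose a ventilator-free day that was actually lived.

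The single line defining ventilation duration also leaves two choices to the programmer: what to do when two records share a calendar day, and whether non-invasive support counts. VFD has a prespecified test and a reported p-value, so two programmers working from the SAP should reach the same score for the same patient. As written, they need not.

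**Working it through.** **The plan's own figure.** The documents give no numerical assumption for VFD. The one sample-size figure is for the primary composite (Protocol 8.7.2: 50% against 30%, two-sided alpha 0.05, 80% power). With pooled variance under the null and no continuity correction:

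n = [1.960 x sqrt(2 x 0.4 x 0.6) + 0.842 x sqrt(0.5 x 0.5 + 0.3 x 0.7)]^2 / 0.2^2 = 93 per group.

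This reproduces the stated 93. VFD does not enter it.

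**Inputs for VFD.** The formula and end dates come from SAP 4.4.2. The patient courses are illustrative assumptions, with randomisation on Day 1 and survivors followed to Day 28.

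**1. Death on ventilation, analysis (b).** Intubated Day 10, dead Day 15.
- Study duration: (15 - 1) - 1 + 1 = 14.
- Ventilation to the date of death, inclusive: 15 - 10 + 1 = 6. VFD = 14 - 6 = 8.
- Days actually free: Days 1-9, which is 9. The score is one day too low.
- Counting distinct calendar days does not help, because Days 10-15 are still six days.
- Ventilation as stop minus start: 15 - 10 = 5. VFD = 14 - 5 = 9, which is correct.

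**2. Survivor, one record, Days 3-12.**
- Days actually free: Days 1-2 and 13-28, which is 2 + 16 = 18.
- Inclusive: 28 - 10 = 18, which is correct.
- Stop minus start: 28 - 9 = 19, one day too many.

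With the end dates as written, inclusive counting is right for case 2 and wrong for case 1. Stop-minus-start counting is the reverse.

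**3. Where the floor hides the error.** Ventilated from Day 1, dead Day 10: 9 - 10 = -1, floored to 0. The correct score is 9 - 9 = 0.

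**4. Records that share a day.** Survivor with non-invasive support Days 3-5, invasive Days 5-12, non-invasive Days 12-14.

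| Counting rule | Ventilation days | VFD |
|---|---|---|
| Per record, inclusive | 3 + 8 + 3 = 14 | 14 |
| Distinct calendar days, any type | 12 | 16 |
| Per record, stop minus start | 2 + 7 + 2 = 11 | 17 |
| Distinct calendar days, invasive only | 8 | 20 |

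**5. Type.** Assume that non-invasive support is recorded as ventilation. Ten such days (Days 3-12) and ten intubated days then both give 28 - 10 = 18. An invasive-only count gives 28 and 18. A patient with no ventilation scores 28 under every rule.

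**6. Effect on the treatment contrast.** Let qA and qB be the shares of each arm who die on ventilation with at least one truly free day. With inclusive counting, the arm means in analysis (b) fall by qA and qB days, and the difference in means moves by qA - qB days, which is less than one day. The documents give no value for either share.

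**The case against.** The strongest reply is that most of this is missing detail in an exploratory endpoint, handled identically in both blinded arms. Much of that stands, and it rules out several stronger readings.

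- **A reader might infer that same-day records are double-counted.** The text allows this but does not say it. SAP 4.3 defines drug exposure by summing days with at least one dose, so a two-dose day counts once. Read in the same way, the ventilation line means distinct days, and case 4 gives 16. The floor at 0 does not prove per-record summing, because the death-date mismatch alone can make ventilation exceed study duration (case 3).
- **A reader might infer that avoiding intubation earns nothing.** That holds only where equally long non-invasive support replaces it and is recorded as ventilation. The documents imply more than one type but never list them. Avoiding ventilation altogether does earn days.
- **A reader might infer that any-type counting is an error.** The protocol's name for this endpoint does not say invasive, while the two neighbouring ventilation endpoints (Protocol 7.2.1, items 6 and 7) do. Counting any ventilation can be a deliberate choice. Invasive ventilation is also isolated in the primary endpoint and in those two secondary endpoints.
- **A reader might infer that every patient ventilated at death is mis-scored.** The error is confined to analysis (b), disappears under the floor, and depends on inclusive counting.
- **A reader might ask that the death-equals-zero version be made the main analysis.** Nothing in these defects calls for that.

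The reply does not remove the mismatch. The two end dates are both explicit, and neither day convention makes them consistent for deaths and survivors together.

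**Conclusion.** The concern holds in limited form. The end dates for deaths are inconsistent as written. With inclusive counting this costs one day per patient who dies on ventilation, in analysis (b) only and only where the score is not floored. The death-equals-zero analysis and the survivor analysis are unaffected by it. Switching to stop-minus-start counting moves the error to survivors.

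The overlap rule and the ventilation type are undefined rather than wrong. For the illustrative three-record course, the any-type counting rules shown give 14 to 17, and an invasive-only count gives 20.

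These sizes rest on assumed patient courses, and the type comparison rests on the further assumption that non-invasive support is entered as ventilation. How often deaths on ventilation or same-day changes occur is not in the documents, so no net bias between arms can be claimed. The primary test and the sample size stand as they are.

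**What to change.** Amend the VFD paragraph of SAP 4.4.2, before unblinding, to state the following.

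1. **One last day for both terms.** For deaths up to Day 28 this is the day before death, and every ventilation record is cut at that day. Otherwise it is the date of study completion or discontinuation.
2. **One convention.** Count inclusively in both terms, with start and stop days both included.
3. **Each calendar day once.** Ventilation duration is the number of distinct days, from randomisation to the last day, with at least one counted record.
4. **Types.** List the eCRF ventilation types that count. Report an invasive-only VFD, using the same type filter as SAP 4.4.1, alongside the any-ventilation version.

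With these rules case 1 gives 9, case 2 gives 18, and case 4 gives 16 for any ventilation and 20 for invasive only. The difference can no longer be negative, so the floor becomes a data check. The existing analyses of deaths and survivors can stay as they are.

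The cost is a few lines of SAP text and derivation code, plus one extra set of VFD outputs. It uses ventilation types and dates already collected, and needs no new data and no change to sample size.
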